### 10.8 Multicenter Studies

This is a multicenter study, having approximately 55 centers participating in the study. The center effects will be investigated in the primary statistical analysis model by including the treatment by investigator type interaction. As exploratory analyses to examine the variability of the treatment effect across centers, the following analyses will be performed:

- Pool the centers into self-standing center pools of at least 18 subjects. The pooling will sort by investigator type and number of randomized subjects. Then, the centers with fewer than 18 subjects will be pooled until the self-standing center pool is at least 18 subjects. The treatment effect will be explored using a logistic model including treatment, household number of randomly assigned subjects, age, baseline lesion counts, BOTE score at Baseline, and a strata statement which will include the pooling identified and examining the residual score statistics. To address treatment by center interaction, each pooling center will have a corresponding variable coded as 1 if on SB206 and 0 otherwise. Some pooled centers may have a p-value of less than 0.05 by chance since there will be multiple pooled centers.

- Pool the centers using the method above but the self-standing center pools will contain at least 12 subjects. This analysis should be interpreted with caution due to the small sample size within pooled centers.

## 11. METHODS OF EFFICACY ANALYSIS

### 11.1 Primary Efficacy Analysis

The primary efficacy comparison will test the following hypotheses:

H0: The proportion of subjects with complete clearance is equal between SB206 10.3% QD and Vehicle;

H1: The proportion of subjects with complete clearance is different between SB206 10.3% QD and Vehicle.

The primary efficacy model will be the following for  $\pi_{H_i}$  as the probability of complete clearance for the  $i^{th}$  subject in household H:

$$\pi_{H_i} = \frac{e^{(\beta_0 + \beta_1 * X_{H_{i1}} + \beta_2 * X_{H_{i2}} + \beta_3 * X_{H_{i3}} + \beta_4 * X_{H_{i4}} + \beta_5 * X_{H_{i5}} + \beta_6 * X_{H_{i6}} + \beta_7 * X_{H_{i7}} + \beta_8 * X_{H_{i8}} + \beta_9 * X_{H_{i9}} + \beta_{10} * X_{H_{i10}} + \beta_{11} * X_{H_{i11}} + \beta_{12} * X_{H_{i12}} + \beta_{13} * X_{H_{i13}})}}{1 + e^{(\beta_0 + \beta_1 * X_{H_{i1}} + \beta_2 * X_{H_{i2}} + \beta_3 * X_{H_{i3}} + \beta_4 * X_{H_{i4}} + \beta_5 * X_{H_{i5}} + \beta_6 * X_{H_{i6}} + \beta_7 * X_{H_{i7}} + \beta_8 * X_{H_{i8}} + \beta_9 * X_{H_{i9}} + \beta_{10} * X_{H_{i10}} + \beta_{11} * X_{H_{i11}} + \beta_{12} * X_{H_{i12}} + \beta_{13} * X_{H_{i13}})}}$$

where H = Household,  $i$  = subject within the household,  $\beta_0$  is the intercept,

$$X_{H_{i1}} = \begin{cases} 1, & \text{if treatment is SB206} \\ 0, & \text{if treatment is Vehicle} \end{cases}$$

$$X_{H_{i2}} = \begin{cases} 1, & \text{if subject is from a 2 subject household} \\ 0, & \text{if subject is from a 1 subject household} \end{cases}$$

$$X_{H_{i3}} = \begin{cases} 1, & \text{if subject is from a Dermatology site} \\ 0, & \text{if subject is from an Other site} \end{cases}$$

$$X_{H_{i4}} = \begin{cases} 1, & \text{if subject has a Baseline BOTE Score of 0} \\ 0, & \text{if subject has a Baseline BOTE Score of } \geq 1 \end{cases}$$

$$X_{H_{i6}} = \begin{cases} 1, & \text{if subject has a baseline age 0 to } < 3 \\ 0, & \text{otherwise} \end{cases}$$

$$X_{H_{i7}} = \begin{cases} 1, & \text{if subject has a baseline age 3 to } < 4 \\ 0, & \text{otherwise} \end{cases}$$

$$X_{H_{i8}} = \begin{cases} 1, & \text{if subject has a baseline age 4 to } < 5 \\ 0, & \text{otherwise} \end{cases}$$

$$X_{H_{i9}} = \begin{cases} 1, & \text{if subject has a baseline age 5 to } <6 \\ 0, & \text{otherwise} \end{cases}$$

$$X_{H_{i10}} = \begin{cases} 1, & \text{if subject has a baseline age 6 to } <7 \\ 0, & \text{otherwise} \end{cases}$$

$$X_{H_{i11}} = \begin{cases} 1, & \text{if subject has a baseline age 7 to } <8 \\ 0, & \text{otherwise} \end{cases}$$

$$X_{H_{i12}} = \begin{cases} 1, & \text{if subject has a baseline age 8 to } <9 \\ 0, & \text{otherwise} \end{cases}$$

$$X_{H_{i13}} = \begin{cases} 1, & \text{if subject has a baseline age 9 to } <12 \\ 0, & \text{otherwise} \end{cases}$$

$X_{H_{i5}}$  is the subject's baseline lesion count; treatment will be included in the class statement with PARAM=REF and REF=Vehicle. The working correlation will have an exchangeable structure. In the event of issues with convergence, an independent structure will be utilized. The model will include a repeated statement for subject household with household ID in the class statement. Also, the data structure will be ordered according to household ID and subject ID in household.

Treatment groups will be compared using a generalized estimating equation for logistic regression with an exchangeable working correlation structure. The model will include treatment, investigator type (dermatologist vs other), household number of randomly assigned subjects (1 subject per household vs 2 subjects per household), BOTE score at Baseline (no inflammation [BOTE=0] vs mild/moderate/severe/very severe inflammation [BOTE≥1]), age (0 to <3, 3 to <4, 4 to <5, 5 to <6, 6 to <7, 8 to <9, 9 to <12, and ≥12 years old), and baseline lesion count as factors. For subjects from a household with 2 subjects, the actual values of BOTE score at Baseline and investigator type will be utilized with the recognition that such subjects did not have further stratification according to investigator type and BOTE score at Baseline. The odds ratio between SB206 10.3% and vehicle gel, 95% confidence intervals for the odds ratio, and *P*-value for the covariate-adjusted treatment comparison will be presented together with predicted proportions along with their associated 95% confidence interval. The difference in proportion confidence interval will be calculated using the following formula:

$$(p_{SB206} - p_{Vehicle}) \pm z_{0.025} * SE$$

Where the SE =

$$\sqrt{\frac{p_{SB206}^2(1 - p_{SB206})^2 s_{SB206}^2 + p_{Vehicle}^2(1 - p_{Vehicle})^2 s_{Vehicle}^2 - 2p_{SB206}(1 - p_{SB206})p_{Vehicle}}{(1 - p_{Vehicle}) * \left( \frac{s_{SB206}^2 + s_{Vehicle}^2 - s_{Odds Ratio}^2}{2} \right)}}$$

The  $p_{SB206}$  and  $p_{Vehicle}$  are the transformed predicted log odds at the mean of the covariates,  $s^2$ 's are the standard errors of the predicted log odds and the odds ratio.

As a sensitivity analysis, the above primary analysis model will be applied to the PP Population. An additional sensitivity analysis counting subjects who discontinued prior to Week 12 or have a missing lesion count assessment but who demonstrated complete clearance at the last collected lesion assessment as responders will be presented. The impact of mis-stratifications may be explored via a sensitivity analysis.

An analysis where the complete clearance response probability for each dropout prior to Week 12 will be independently generated across the following scenarios (Vehicle response probability, SB206 response probability):

(0.1, 0.1)	(0.1, 0.0)			
(0.2, 0.2)	(0.2, 0.1)	(0.2, 0.0)		
(0.3, 0.3)	(0.3, 0.2)	(0.3, 0.1)	(0.3, 0.0)	
(0.4, 0.4)	(0.4, 0.3)	(0.4, 0.2)	(0.4, 0.1)	(0.4, 0.0)

The analysis will be produced 100 times and then the results for the estimated log odds ratio for treatment and its estimated standard error from each of the imputations will be combined using PROC MIANALYZE.

An additional sensitivity analysis will be performed in a subset of the ITT population where only 1 subject from each household is chosen to contribute to the model based on the subject with the highest number of baseline treatable MC and the oldest to break ties, if needed. A logistic regression model including treatment, investigator type, BOTE score at Baseline, age, and baseline lesion counts will be utilized.

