## 5. DETERMINATION OF SAMPLE SIZE

Approximately 850 subjects, 6 months of age and older, with a minimum of 3 and a maximum of 70 MC lesions at Baseline will be randomized in a 1:1 (active:vehicle) scheme. The sample size assumptions for this study were informed by the integration of the completed phase 3 studies [NI-MC301](#) and [NI-MC302](#). Multiple replications of simulated random sampling of the integrated NI-MC301 and NI-MC302 data was performed to ensure the sample size assumptions align with the proposed design of NI-MC304. This includes the 1:1 ratio (active:vehicle) and the percentages observed in NI-MC301 and NI-MC302 for each stratum of each of the stratification factors: investigator type, number of randomized subjects per household, and baseline BOTE score that are planned for NI-MC304.

The analysis of the proportion of subjects with complete response of all treatable MC at Week 12 within the Intent-to-Treat (ITT) Population of the multiple replications of simulated random sampled integrated data yields rates of 20% for vehicle and 29.5% for SB206 10.3% QD with the covariate-adjusted treatment difference was 9.5%. A sample size of 850 subjects (425 subjects in the SB206 10.3% QD group and 425 subjects in the vehicle group) will provide 90% power for a 2-sided alpha test of size 0.05 to detect an absolute difference of 9.5% when the vehicle response rate is 20%.

Simulations were performed with 10,000 replications to confirm the accuracy of these power estimates (i.e., true power and simulation based estimate of power) and to provide simulated median, 10% percentile and lowest detectable treatment difference estimates for a sample size of 850 subjects.

At the two-sided  $\alpha=0.05$  level, the median detectable treatment difference is approximately 9.9% with a simulation based estimated power of 88%. The tenth percentile for detectable treatment difference is 7.1%, thus approximately 90% of the simulations with two-sided  $p < 0.05$

produced an estimated treatment difference exceeding 7.1%. The lowest detectable treatment difference is 5.7%.

At two-sided alpha levels  $<0.05$ , for example,  $p=0.025$  level, the median detectable treatment difference is approximately 10.2% with a simulation based estimated power of 82%. The tenth percentile for detectable treatment difference is 7.7% and a lowest detectable difference of 6.5%.

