## 10.3 Adjustments for Covariates

The model for the primary efficacy will include adjustments for the following covariates: investigator type (dermatologist vs other), household number of randomized subjects (1 subject per household vs 2 subjects per household), BOTE score at Baseline (no inflammation [BOTE=0] vs mild/moderate/severe/very severe inflammation [BOTE $\geq$ 1]), age (0 to <3, 3 to <4, 4 to <5, 5 to <6, 6 to <7, 8 to <9, 9 to <12, and  $\geq$ 12 years old), and baseline lesion count. If there are not at least 3 responders and non-responders at each level of the stratification factors, then that stratification factor will be removed from the model. If there are fewer than 10 responders/non-responders, then neither investigator type nor household number of randomized subjects nor BOTE score at Baseline will be included in the model.

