## 11.2 Secondary Efficacy Analyses

The secondary endpoints of the proportion of subjects achieving a lesion count of 0 or 1 of all treatable MC at Week 12, proportion of subjects achieving at least a 90% reduction from Baseline in the number of all treatable MC at Week 12, and the proportion of subjects with complete clearance of all treatable MC at Week 8 will be analyzed in the same manner as the primary endpoint.

Since the within-household correlation is expected to be small, the percent change from Baseline in the number of all treatable MC at Week 4 will be analyzed using a repeated measures mixed model for the respective visits with the same covariates as the primary model together with visits and treatment by visit interaction; an unstructured covariance matrix will be utilized. If the calculation of the percent change from baseline is influenced by outliers with calculated values >100%, then the influence of outliers will be avoided for analysis by censoring them so that all values were in the range of -100% to 100%. If the model fails to converge, then other correlation structures will be explored.

A sensitivity analysis using the PP Population will be provided for the proportion of subjects achieving a lesion count of 0 or 1 of all treatable MC at Week 12 and the proportion of subjects achieving at least a 90% reduction from Baseline in the number of all treatable MC at Week 12.

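### The SAP's age lists skip ages 7 to under 8 although the primary-model equation includes them, and the variance terms in the difference-in-proportions interval are defined on the wrong scale

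*SAP*

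**What the plan says.** **Age coding.** SAP 11.1 introduces its equation with "The primary efficacy model will be the following". Its age terms run from X_Hi6 to X_Hi13, and X_Hi11 equals 1 "if subject has a baseline age 7 to" under 8. That makes eight indicators with 12 years and over as the implied reference, so nine contiguous bands.

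The prose gives eight bands. The list in 11.1 reads "5 to <6, 6 to <7, 8 to <9, 9 to <12, and ≥12 years old"; SAP 10.3 has the same sequence ("5 to <6, 6 to <7, 8 to <9, 9 to <12, and" then the oldest group), and so does step 2 of the multiple imputation in SAP 10.4. SAP 11.2 analyses three secondary endpoints in the same way as the primary and models the fourth "with the same covariates as the primary model together with visits and treatment by visit interaction".

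**Interval for the difference.** SAP 11.1 forms the interval as the difference in predicted proportions plus or minus z times SE. The SE uses three s-squared terms, with subscripts SB206, Vehicle and Odds Ratio. The text below the formula says that these terms "are the standard errors of the predicted log odds and the odds ratio".

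**The concern.** The covariate coding of a primary model should have only one reading before unblinding. Here a programmer can follow the equation or the list, and they differ for children aged 7. Mean ages in the two previous phase 3 studies were 7.1 and 6.5 years (Protocol 2.1), so the missing band lies in the middle of the expected age range. The list can be implemented in two ways:

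- As a class variable, it gives 7-year-olds a missing covariate, and a regression procedure drops them by default from an analysis meant to include everyone randomized.
- As indicators, it places them in the reference group with subjects aged 12 and over.

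For the imputation model the list is the only age specification.

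The interval formula raises a different issue. It is the only interval the SAP specifies for the absolute difference, which is the scale on which the trial was sized. If its inputs are taken as defined, the interval is too wide and can include zero beside a clearly significant primary P-value.

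**Working it through.** **Inputs** (SAP 5): 425 per arm, vehicle 20%, SB206 29.5%, two-sided alpha 0.05, stated power 90%.

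**The plan's own figure.** Pooled-variance two-proportion test, mean rate 0.2475:

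- null SE = sqrt(2 × 0.2475 × 0.7525 / 425) = 0.0296
- alternative SE = sqrt(0.295 × 0.705/425 + 0.2 × 0.8/425) = 0.0294
- power = Φ((0.095 − 1.96 × 0.0296)/0.0294) = 89.6%, in agreement with the stated 90%.

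**(a) Age bands.** Setting the listed bands end to end (0–3, 3–4, 4–5, 5–6, 6–7, 8–9, 9–12, 12+) leaves one gap, 7 to 8, the same in all three lists.

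The documents give no share of 7-year-olds, so 5 to 15% is assumed: 0.05 × 850 = 42.5 and 0.15 × 850 = 127.5, or about 43 to 128 subjects. If they are dropped:

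| Share aged 7 | n per arm | Power |
|---|---|---|
| none dropped | 425 | 89.6% |
| 5% | 403.75 | 88.0% |
| 15% | 361.25 | 84.2% |

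Simulated logistic fits (1,500 trials, 10% aged 7, no age effect) compare the three possible codings:

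| Coding | Mean log OR | SE | Power |
|---|---|---|---|
| Equation (nine bands) | 0.518 | 0.163 | 89.3% |
| 7-year-olds merged into 12+ reference | 0.517 | 0.163 | 89.5% |
| 7-year-olds dropped (mean n 765) | 0.517 | 0.172 | 85.6% |

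With no age effect, merging costs nothing and dropping costs precision. Merging when age does affect clearance was not examined.

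**(b) Difference interval.** Write w = p(1−p), and let V1, V2 be the variances of the two predicted log odds. The delta method gives

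Var(p1 − p2) = w1²V1 + w2²V2 − 2·w1·w2·Cov.

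Because the log odds ratio is the difference of the two log odds, V_logOR = V1 + V2 − 2Cov, so Cov = (V1 + V2 − V_logOR)/2. The SAP formula has this form, taking the break in its printed display as a line wrap. It is right if each s-squared is a variance and the third is the variance of the **log** odds ratio.

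At the planning rates:

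- w1 = 0.295 × 0.705 = 0.2080; w2 = 0.2 × 0.8 = 0.16
- V1 = 1/(425 × 0.2080) = 0.01131; V2 = 1/(425 × 0.16) = 0.01471
- V_logOR = V1 + V2 = 0.02602; SE(log OR) = 0.161
- OR = (0.295/0.705)/(0.2/0.8) = 1.674; SE(OR) = 1.674 × 0.161 = 0.270
- log-OR Wald z = ln(1.674)/0.161 = 3.19, p = 0.0014

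| Reading of the s-squared terms | SE of difference | 95% CI (points) |
|---|---|---|
| Variances, log OR (correct) | 0.0294 | 3.7 to 15.3 |
| Variances, third on OR scale | 0.0493 | −0.2 to 19.2 |
| Standard errors entered, log OR | 0.0741 | −5.0 to 24.0 |
| Standard errors entered, OR scale (fully literal) | 0.0955 | −9.2 to 28.2 |

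The correct reading equals the direct SE, sqrt(0.2080/425 + 0.16/425) = 0.0294. The OR-scale readings widen the interval by 0.0493/0.0294 = 1.7 times and, fully literal, 0.0955/0.0294 = 3.2 times.

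**How often this would show.** With vehicle at 20%, the log-OR Wald test is significant from a difference of 5.65 points; SAP 5 says "The lowest detectable treatment difference is 5.7" percent. With the OR-scale variance, the lower limit reaches zero only at 9.82 points. SAP 5 also says "the median detectable treatment difference is approximately 9.9" percent, so about half of significant trials fall below that point. In 200,000 simulated trials at 29.5% vs 20%, power was 89.5%, and the median and tenth percentile of significant differences were 9.9 and 7.1 points, both as in SAP 5. The OR-scale interval included zero in 48.7% of the significant trials; the correct interval did so in none.

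**The case against.** On age, the equation is explicit and complete, the listed bands are otherwise contiguous, and the intended list is hardly in doubt. Secondary analyses that take their covariates from the primary model can be read as taking them from the equation. Dropping 7-year-olds would contradict the ITT definition in SAP 8, and the independent double programming in Appendix B, or simply the analysis N, should expose the loss. Only the imputation model has no equation to fall back on, and that is one sensitivity analysis.

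On the interval, the algebra is right, the symbols are already squared, and the first two terms are on the log-odds scale, so an experienced programmer would probably infer the log odds ratio. The 48.7% describes one particular misreading, not the plan itself. The interval decides nothing, and the primary analysis in Protocol 10.3.1 does not ask for it.

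Most of this stands as an argument about likelihood: the equation shows intent, the losses arise only if the text is followed, and the primary test does not depend on the interval. It does not remove either defect. The omission occurs three times, once in the section that holds the equation, and the formula's definitions give a wrong interval when applied as stated. A pre-specified analysis should not rely on the programmer to correct it.

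**Conclusion.** Both defects hold and should be fixed before unblinding.

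- **Age lists.** The SAP gives two codings for its primary model. One loses nobody. Of the two ways to implement the other, the class variable drops about 43 to 128 subjects and lowers power to between 88.0% and 84.2%. That rests on the assumed 5 to 15% share aged 7 and on building the class variable from the list. The indicator version is harmless when age has no effect, the only case tested.
- **Difference interval.** At the planned effect, the stated definitions turn an interval of 3.7 to 15.3 points into one that includes zero: −0.2 to 19.2 if only the odds-ratio scale is taken literally, −9.2 to 28.2 if both slips are. These figures use the planning rates without covariates. The odds ratio, its interval and the primary P-value are not affected by this slip.

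**What to change.** 1. Insert 7 to <8 in the age lists of SAP 10.3, 10.4 (multiple imputation, step 2) and 11.1, so that they match the equation.
2. In the SE formula of SAP 11.1, relabel the last term as the log odds ratio.
3. In the sentence that defines the s-squared terms, state that each is the squared standard error (variance) of the predicted log odds in each arm and of the log odds ratio.

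The cost is a few words in the SAP before unblinding. Data collection, sample size and the primary test do not change.

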10 ANALYSIS

10.1 Hypothesis

This study is intended to formally evaluate the efficacy of SB206 10.3% QD against Vehicle.

The primary efficacy comparison will test the following hypotheses:

H0: The proportion of subjects with complete clearance is equal between SB206 10.3% QD and Vehicle;

H1: The proportion of subjects with complete clearance is different between SB206 10.3% QD and Vehicle.

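### Adjusted clearance proportions are computed at the mean of the covariates, so they do not estimate the average clearance probability and will usually read low in both arms

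*SAP*

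**What the plan says.** The null hypothesis in Protocol 10.1, repeated in SAP 11.1, is about proportions of subjects: "The proportion of subjects with complete clearance is equal between SB206 10.3% QD and Vehicle". The sample size section of the SAP works on the same scale: its resampling of the two earlier phase 3 studies "yields rates of 20% for vehicle and 29.5% for SB206 10.3% QD".

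For the analysis, SAP 11.1 states: "Treatment groups will be compared using a generalized estimating equation for logistic regression with an exchangeable working correlation structure". The covariates are household number, investigator type, Baseline BOTE category, age band and baseline lesion count. All except lesion count enter as 0/1 indicators. The output is the odds ratio with its interval and P-value, plus predicted proportions. The SAP adds: "The difference in proportion confidence interval will be calculated using the following formula". The two proportions in that formula "are the transformed predicted log odds at the mean of the covariates".

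Neither document specifies a standardised estimate, that is, one averaged over subjects. Protocol 10.3.1 does require the observed number and percentage with complete clearance by treatment group. SAP 11.2 and 11.3 send three secondary responder endpoints and several exploratory ones through the same analysis.

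**The concern.** With a logit link, the probability at average covariates and the average of the subjects' probabilities are different quantities. The plan's hypothesis and planning rates are about the second; the reported adjusted proportions are the first. Because most covariates are indicators, the mean profile is fractional (part dermatology site, part other; a share of each age band) and matches no subject.

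At stake is how the adjusted rates read in the report. A reader will compare them with 20% and 29.5%, with the raw percentages beside them, and with the earlier studies' rates. If both adjusted rates sit below their raw counterparts only because of where the curve was evaluated, that needs an explanation the plan does not supply. The same would happen in every responder table that inherits the method.

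**Working it through.** **Inputs.** From SAP 5: rates of 20% and 29.5%, 425 per arm, two-sided alpha 0.05, 90% power. From SAP 11.1: logistic link, proportions taken at the covariate means. Not in the documents: the SD of the covariate part of the linear predictor (called σ here, on the log-odds scale). It is assumed and varied.

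**1. The plan's own power figure.** The unpooled standard error is √[(0.20×0.80 + 0.295×0.705)/425] = 0.0294. Then 0.095/0.0294 = 3.23, and 3.23 − 1.96 = 1.27, which gives power 89.8%. The version with a pooled null variance gives 89.6%. The stated 90% reproduces, and it does not depend on how the adjusted proportions are computed.

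**2. Why the two quantities differ.** Let p be the inverse-logit at the mean linear predictor. To second order,

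average probability ≈ p + ½·p(1−p)(1−2p)·σ².

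For p below 50% the added term is positive, so p lies below the average. With σ = 0.5:
- Vehicle: p = 0.1887; ½×0.1887×0.8113×0.6226×0.25 = 0.0119; sum 0.2006.
- SB206: p = 0.285; ½×0.285×0.715×0.430×0.25 = 0.0110; sum 0.2960.

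So at-mean values of about 18.9% and 28.5% correspond to average rates of about 20% and 29.5%.

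**3. Exact calculation.** For each arm the intercept was solved so that the average probability equals 20% or 29.5%; the inverse-logit was then evaluated at the mean linear predictor. Two assumed shapes were used: a normal predictor, and one in which clearance falls with a right-skewed lesion count (range 3 to 70, mean about 18; Protocol 2.1 gives means of 18.1 and 18.3 in the earlier studies but no spread).

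| σ (assumed) | Normal: vehicle / SB206 (difference) | Falling with lesion count: vehicle / SB206 (difference) |
|---|---|---|
| 0.25 | 19.7 / 29.2 (9.5) | not run |
| 0.5 | 18.9 / 28.5 (9.6) | 18.9 / 28.4 (9.5) |
| 0.8 | 17.3 / 27.1 (9.8) | 17.5 / 26.9 (9.4) |
| 1.0 | 16.1 / 26.0 (9.9) | 16.5 / 25.6 (9.1) |
| 1.3 | 14.1 / 24.1 (10.0) | 14.7 / 23.5 (8.8) |

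The averaged rates are 20.0 / 29.5 (9.5) in every row by construction.

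**4. Fitted trials.** For each of four lesion-count slopes, 400 trials of 850 subjects were simulated and fitted by ordinary logistic regression with the SAP covariates (no household clustering). The at-mean proportion was below the averaged one in both arms in every trial. Mean values ranged from 19.3 / 28.6 at-mean against 20.1 / 29.3 averaged (no lesion-count effect) to 17.0 / 26.2 against 20.3 / 29.5 (steepest slope).

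**5. Limits of the direction.** The logistic curve is convex only where the linear predictor is below zero. If 3% of subjects have log odds higher by 5, the at-mean values are 19.9 / 30.5, so the SB206 rate is overstated. With log odds higher by 6 they are about 20.3 / 31.1, so both are overstated. If clearance instead rose with lesion count, the rates still read low but the difference widened, reaching 11.4 points at σ = 1.38.

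**The case against.** The strongest reply is that nothing decisive rests on these proportions. Success is judged on the GEE treatment P-value, and neither it nor the odds ratio uses them. In the model as written in SAP 11.1, without a treatment interaction, the at-mean difference is zero exactly when the averaged difference is zero, so the null hypothesis is the same. The SAP says openly where the proportions are evaluated, and its interval applies the delta method to those same quantities, so the method is coherent in itself. It also does not say whether its planning figure ("covariate-adjusted treatment difference was 9.5" points) was averaged or taken at the mean. Observed rates are reported as well, and with weak covariates the gap is a few tenths of a point.

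All of that stands, and it makes this a reporting matter rather than a flaw in the test. It does not make the at-mean values estimates of the proportion of subjects who clear.

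A reader might infer three stronger things, none of which the documents support:
- That at-mean rates below 50% are always too low. Step 5 of the working gives counterexamples, although they need a small group with near-certain clearance.
- That the treatment difference is understated. It rises in some cases and falls in others.
- That power or the primary test is compromised. The planned power reproduces, and the test does not involve these values.

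**Conclusion.** The point holds as a matter of estimation and reporting, at low severity. At the planning rates and with realistic covariate distributions, the adjusted proportions will usually fall below the average clearance probability in both arms: by about 0.3 points at σ = 0.25, about 1 point at 0.5 and 3.5 to 4 points at 1.0. The last figure would be noticeable beside a planned effect of 9.5 points. The difference is less sensitive: about 8.8 to 10.0 points for σ up to 1.3 with a normal predictor or with clearance falling as lesion count rises, and wider if clearance rose with lesion count.

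The size rests entirely on σ and on the shape of the predictor, which the documents do not give. The direction rests on rates below 50% and on the absence of an extreme subgroup. The size will also vary by endpoint, because the gap depends on the response rate.

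**What to change.** In SAP 11.1, replace the at-mean definition. From the same fitted GEE, predict each ITT subject's clearance probability once as if on SB206 and once as if on vehicle, keeping that subject's own covariates. Average each set, and report the two standardised proportions and their difference. Obtain the interval by the delta method from the household-clustered robust covariance matrix. Apply the same definition to the secondary and exploratory responder endpoints analysed like the primary. The odds ratio, its interval and the P-value stay as planned, as do the raw percentages.

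The cost is a few lines of code beyond the default software output, and reported rates that differ from that default. Protocol 10.3.1 asks only for predicted proportions, so a SAP clarification before unblinding appears sufficient. If the sponsor prefers to keep the at-mean values, they should be labelled as such in the tables and the standardised rates shown beside them.
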